### 8.3.5 ADVERSE EVENT REPORTING

Following initiation of study treatments, all AEs, regardless of cause or relationship, throughout the duration of the study will be reported on the eCRFs.

### 8.3.6 SERIOUS ADVERSE EVENT REPORTING

All SAEs, regardless of cause or relationship, that occur after the participant first consents to participate in the study (i.e. the signing of the informed consent) and throughout the duration of the study will be reported on the eCRFs.

The medical monitor will immediately report to Defined Research any SAE, whether or not considered study intervention related, and will include an assessment of whether there is a reasonable possibility that the study intervention caused the event. Study endpoints that are SAEs (e.g., all-cause mortality) must be reported in accordance with the protocol. All SAEs will be followed until satisfactory resolution or until the study investigator deems the event to be chronic or the participant is stable.

### 8.3.7 REPORTING EVENTS TO PARTICIPANTS

Not applicable.

### 8.3.8 EVENTS OF SPECIAL INTEREST

Events of special interest include all reports of medication error, abuse, misuse, overdose, and product complaints with AE. Medication error is any unintentional error in the prescribing, dispensing, preparation for administration or administration of an investigational product while the medication is in the control of a health care professional, patient, or consumer.

Medication errors may be classified as a medication error without an AE, which includes situations of missed dose; medication error with an AE; intercepted medication error, or potential medication error.

Abuse is defined as persistent or sporadic intentional excessive use of an investigational product by a participant.

Misuse is defined as any intentional and inappropriate administration of an investigational product that is not in accordance with the protocol instructions or the local prescribing information.

An overdose is defined as an accidental or intentional administration of a quantity of an investigational product given per administration or cumulatively which is above the maximum recommended dose as per protocol or in the product labelling (as it applies to the daily dose of the participant in question). In cases of a discrepancy in drug accountability, overdose will be established only when it is clear that the participant has taken the excess dose(s). Overdose cannot be established when the participant cannot account for the discrepancy except in cases in which the investigator has reason to suspect that the participant has taken the additional dose(s).

Product complaint is defined as complaints arising from potential deviations in the manufacturing, packaging, or distribution of the investigational product.

### 8.3.9 REPORTING OF PREGNANCY

Not applicable.

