## 4 STUDY DESIGN

### 4.1 OVERALL DESIGN

We hypothesize that Defined CBD, a novel CBD-based formulation in the form of a small orally administered capsule, will increase the percentage of time participants spend in deep (SWS) and REM sleep, as measured by an objective sleep-tracking device called “Whoop”. Our research study, entitled Le Rêve 3.0, is a double-blind, placebo-controlled, randomized, crossover investigational study to determine if Defined CBD, a Custom-Formulated CBD Capsule, influences sleep physiology. This capsule contains no Δ-9-THC. As this study is only designed to evaluate the effects of Defined CBD on the structure and function of sleep physiology, the phase of the trial is not applicable. This trial is not intended to treat, diagnose, prevent, or cure any disease.

The Le Rêve 3.0 study will involve a cross-over design in which study participants will cycle through two independent treatments, each for four weeks (Treatment 1: Placebo; Treatment 2: Defined CBD). The placebo will look, smell and taste the same as the Defined CBD capsule. The study participants will initially be randomized with respect to the treatment arm, and every participant will cycle through both treatment arms. We will use a double-blind design in which the investigator and study participants will both be blinded to the treatments. Baseline data for each participant will be collected for two weeks prior to initiating treatments, as well as for a one-week washout period following each treatment arm. The entire study duration will be 12 weeks (for Schema see section 1.2).

Primary data for Le Rêve will be obtained in a completely unbiased manner from a non-invasive sleep-tracking wrist-worn device called “Whoop” (<https://www.whoop.com>), that electronically collects and transmits sleep data from study participants in the comfort of their own beds.

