### 5 STUDY POPULATION

#### 5.1 INCLUSION CRITERIA

In order to be eligible to participate in this study, an individual must meet all of the following criteria:

- 1) Has provided a signed and dated informed consent form.
- 2) Presence of chronic insomnia defined as self-reported difficulty initiating (latency to persistent sleep >30 min) and/or maintaining sleep (>30 mins awake during the middle of the night, or waking >30 mins before desired waking time on three or more nights per week) for at least 3 months.
- 3) Insomnia Severity Index score >15.
- 4) Male or female aged 25–70 years.
- 5) Is willing to comply with *all* study procedures throughout the entire study, including:
  - Wearing a sleep-tracking device on their wrist throughout entire clinical study.
  - Ensuring that the sleep-tracking device is connected to their smartphone via Bluetooth on a daily basis so that sleep data can be collected on a daily basis.
  - Ensuring that the sleep-tracking device is charged before going to bed each night, ensuring that sleep data can be collected on a daily basis.
  - Is willing to receive and respond to daily text (SMS) notifications for the duration of the entire clinical study.
  - During the treatment phases of the study, is willing to take the treatment for at least four nights in each week.
- 6) On the nights in which the participant takes the treatment, is willing to abstain from excessive alcohol intake (>two drinks/day).

7) On the nights in which the participant takes the treatment, is willing to refrain from drinking alcohol two hours before bedtime.

8) Female subjects who:

-Are postmenopausal, with amenorrhea for at least one year before the screening interview, OR

-Are surgically sterile, OR

-If of childbearing potential agree to practice effective double barrier methods of contraception (e.g., condom + diaphragm; condom or diaphragm + spermicidal gel or foam), from the time of the signing of informed consent through the last dose of study treatment, or agree to completely abstain from intercourse.

9) Self-reported bedtime between 9 pm and midnight on four-seven nights per week.

10) Owns a smartphone.

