- 19) Inability to refrain from use of any of the following contra-indicated drugs for at least one week prior to and for the duration of the study: erythromycin, clarithromycin, itraconazole, ketoconazole, posaconazole, voriconazole, ritonavir, telaprevir, boceprevir, amlodipine, gemfibrozil, cyclosporine, danazol, amiodarone, verapamil, diltiazem, rifampin, theophylline, tizanidine, bupropion, efavirenz, diflunisal, propofol, fenofibrate, lamotrigine, morphine, lorazepam, diazepam, clobazam, stiripentol, valproate, everolimus, sirolimus, or tacrolimus, niacin (vitamin B3 greater than 1g/ day), grapefruit juice.
- 20) Consumption of xanthine-containing beverages (i.e., tea, coffee, energy drinks or cola) of more than five cups or glasses per day.
- 21) Inability to refrain from greater than 400mg/day of caffeine consumption for study duration.
- 22) Participation in any other clinical trial within 30 days before the screening visit.
- 23) Night shift workers (during the 12 months prior to the study and during the study).
- 24) Individuals who nap three or more times per week over the preceding month.
- 25) Current delayed sleep phase syndrome where wake-up time is regularly (>5x/week) later than 9:00 a.m.
- 26) Individuals having to travel across more than two time zones or outside of their country of residence at any time during the study.
- 27) Females who are pregnant, are planning to become pregnant, or are breastfeeding.

28) History of allergies particularly to plant-based products containing terpenes, i.e. flavors and aromatic natural oils for example citrus, mango, lavender, thyme, cedarwood and pine products.

29) Known hypersensitivity to cannabinoids, including CBD.

30) Individuals may be excluded from participating in the study based on the investigator's professional judgement.

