### 8.3.2 DEFINITION OF SERIOUS ADVERSE EVENTS (SAE)

A SAE is defined as an event that, at any dose, results in the following:

- Death.
- Life-threatening (Note: The term “life-threatening” in the definition of “serious” refers to an event in which the participant was at risk of death at the time of the event; it does not refer to an event that hypothetically might have caused death if it were worse or more severe).

- New patient hospitalization due to the investigational product.
- Persistent or significant disability/incapacity.
- A medically important event or reaction: such events may not be immediately life-threatening or result in death or hospitalization but may jeopardize the participant or may require intervention to prevent one of the other outcomes constituting SAEs. Medical and scientific judgement must be exercised to determine whether such an event is a reportable under expedited reporting rules. Examples of medically important events include intensive treatment in an emergency room or at home for allergic bronchospasm; blood dyscrasias or convulsions that do not result in hospitalization; and development of drug dependency or drug abuse.

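### Section 8.3.9 sets pregnancy reporting aside although women who could conceive are enrolled and given active product; no provision requires a pregnancy to be recorded, reported or followed

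*Combined protocol and SAP*

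**What the plan says.** The whole text of section 8.3.9 is "Not applicable".

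Section 5.1 sets eligibility as "Male or female aged 25–70 years". For women who are neither postmenopausal nor surgically sterile, inclusion criterion 8 reads "If of childbearing potential agree to practice effective double barrier methods of contraception", with complete abstinence as the alternative. The barrier requirement runs "from the time of the signing of informed consent through the last dose of study treatment". Exclusion 27 in section 5.2 keeps out "Females who are pregnant, are planning to become pregnant, or are breastfeeding".

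Section 4.1 describes two four-week treatments, one placebo and one Defined CBD, and says that "every participant will cycle through both treatment arms".

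Section 8.3.8 sets out a further class of reportable events: "Events of special interest include all reports of medication error, abuse, misuse, overdose, and product complaints with AE". Pregnancy is not among them.

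**The concern.** To call pregnancy reporting inapplicable is coherent only if no participant can conceive. Criterion 8 says otherwise: it foresees women who could become pregnant and asks them to prevent it while they are on study product. The protocol thus treats pregnancy as an exposure to avoid, but gives the team no instruction for the case in which prevention fails.

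At stake is the completeness of the safety record. An uncomplicated pregnancy exposed to the product has no required form, no required recipient and no required follow-up. The safety summary could say nothing about it without anyone having departed from the protocol.

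**Working it through.** There is no figure in the plan to reproduce and no test or formula involved. The check is whether any other section supplies the duty that 8.3.9 leaves out.

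1. **Can a pregnancy occur on study product?** Yes. Section 5.1 admits women from age 25, including those of childbearing potential. Exclusion 27 acts at entry. The schedule of activities in section 1.3 shows no pregnancy check, and section 5.4 describes a target population that judges for itself whether it meets the criteria.

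2. **Who is exposed?** In principle everyone, because nobody is assigned placebo alone. With 150 enrolled (sections 1.1 and 8.1), planned active exposure is at most 150 × 4 = 600 participant-weeks. Among the 100 participants on whom section 9.2 bases its power, it is 100 × 4 = 400. Both figures include men and women who cannot conceive, so they are ceilings. The share that matters is not stated.

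3. **AE definition (8.3.1).** It covers untoward medical occurrences in a participant. Pregnancy is not named, and a fetus or newborn is not a participant.

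4. **SAE list (8.3.2).** It opens "A SAE is defined as an event that, at any dose, results in the following" and then gives death, danger to life, hospitalization caused by the product, lasting disability and medically important events. It has no item for congenital anomaly or newborn outcome.

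5. **Events of special interest (8.3.8).** The list goes beyond adverse events, since a missed dose without any AE is classed as a medication error. The protocol therefore does collect non-AE events where it chooses to, but pregnancy is not one of them.

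6. **Discontinuation and withdrawal (7.1, 7.2).** Pregnancy is not mentioned. The reason for leaving is recorded, so a pregnancy would appear only if a participant left and gave it as the reason.

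7. **Daily contact (10.1.7).** Text messages serve compliance and the capture of AEs and SAEs. Pregnancy is not named.

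8. **Follow-up (8.3.4) and end of data collection (4.4).** Follow-up concerns AEs and SAEs, with at most three contacts by the medical monitor. Data collection closes at the end of week 12. The second treatment period runs through week 11, which leaves 12 − 11 = 1 week after the last possible dose. A conception late in that period may be recognised only after collection has closed, and its outcome would come months later.

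9. **Safety dataset (9.3).** It is built from AE and SAE forms, so an uncomplicated pregnancy has no place in it.

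10. **Unanticipated problems (8.4).** The contents page lists this section, but the body passes directly from 8.3.9 to section 9, so it offers no fallback.

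No section supplies the missing duty. Items 3, 4, 6 and 7 leave incidental routes only.

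**The case against.** The best case on the other side has four parts.

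- **Other routes exist.** A reader might infer from 8.3.9 that any on-study pregnancy would go unrecorded and unreported. The documents do not support that. Withdrawal reasons are collected, participants are contacted daily, all AEs are recorded whatever their cause, and the SAE definition has a broad medically-important category whose events go to the sponsor at once. A lapse in contraception might also surface as a protocol deviation under 10.1.10. This stands, and it limits the finding to the absence of any requirement. None of these routes requires the pregnancy itself to be reported or followed to outcome.

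- **It may be an unfilled template heading.** The same two words appear under concomitant therapy, rescue medicine, baseline statistics and several other headings. A reader might infer a deliberate decision not to collect pregnancies; the text does not show one, and nothing forbids recording a pregnancy. But whatever its origin, the entry conflicts with criterion 8, and staff would work from it as written.

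- **The consent form may cover it.** Consent pages are not in the review copy and may ask participants to notify the team. That could help a report arrive, but it would not reconcile 8.3.9 with 5.1.

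- **Few events are likely.** Women planning pregnancy are excluded, contraception or abstinence is required through the last dose, and active treatment lasts four weeks. This is fair, and it bears on the weight of the point rather than on whether it is correct.

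The missing item in 8.3.2 is a different matter: an omission that contradicts no other text. It is therefore kept as a secondary point.

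**Conclusion.** The conflict between sections 5.1 and 8.3.9 is real. As written, no provision requires a pregnancy during the study to be recorded, reported or followed to outcome. The finding goes no further than that: a pregnancy might still become known by one of the incidental routes.

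Its size cannot be put as a number of expected pregnancies, because the protocol gives neither the number of women of childbearing potential nor a rate. Active exposure is bounded above by 600 participant-weeks over all participants, and the relevant part is smaller by an unknown amount. The primary and secondary efficacy analyses and the sample size are untouched.

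The conclusion assumes that the text of 8.3.9 is complete, which its intact heading and body suggest, and that no instruction outside the reviewed text overrides it. It is a modest gap in safety data collection, and easy to close before enrolment.

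**What to change.** Reconcile 5.1 and 8.3.9 by replacing the present entry in 8.3.9 with a reporting rule:

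- Any pregnancy the team learns of from consent onward is recorded on an eCRF. This includes one conceived during the study but recognised after week 12.
- The report goes to the sponsor and the independent safety monitor, within a time that the sponsor states.
- The pregnancy is followed to outcome, and the outcome is recorded.

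The daily text contact can serve as one way in. If the sponsor holds that pregnancy reporting truly does not apply, 8.3.9 should explain why in view of criterion 8.

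As a separate change, add a congenital anomaly or newborn outcome item to the list in 8.3.2, so that such an outcome has a defined reporting route.

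The cost is protocol wording, one form, and follow-up contact with any woman affected. That contact would run well past the 12 weeks of participation and could outlast the 20-week study timeline in section 1.1, so it needs a named owner. Clinical handling of a pregnancy is left to the responsible physicians.

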## 9 STATISTICAL CONSIDERATIONS

### 9.1 STATISTICAL HYPOTHESES

The primary objective of the study is:

- To determine if Defined CBD influences objective measures of sleep physiology.

The secondary objective of the study is:

- To determine if Defined CBD influences subjective measures of sleep physiology.

The primary endpoint of the study is:

- To determine if Defined CBD increases the percentage of sleep spent in deep [slow wave sleep (SWS)] and rapid eye movement (REM) sleep as quantified with an objective wrist-worn sleep-tracking device called Whoop.

The null hypothesis is that there is no difference in the percentage of sleep spent in deep and REM sleep in participants that received Defined CBD

and the placebo control; the alternative hypothesis is that there is a difference among the two treatment groups. The difference in the percentage of sleep spent in deep and REM sleep in participants that received Defined CBD and the placebo control at the end of the two four-week treatment phases will be compared using a 2-sided test with an alpha level at 0.05 to evaluate superiority. The p-value and 95% confidence interval for the estimate of treatment difference in percentages will be estimated and constructed using the above-mentioned method.

The secondary endpoints of the study are:

- To determine if Defined CBD changes total sleep time, sleep latency, the number of sleep disturbances, time spent in each sleep stage, and the percentage of time spent in each sleep stage as quantified with the Whoop sleep-tracking device, and subjective measures of sleep physiology as collected via participant surveys.

The null hypothesis is that there is no difference in the secondary endpoints in the study in participants that received Defined CBD and the placebo control; the alternative hypothesis is that there is a difference among the two treatment groups. The difference secondary endpoints in participants that received Defined CBD and the placebo control at the end of the two four-week treatment phases will be compared using a 2-sided test with an alpha level at 0.05 to evaluate superiority. The p-value and 95% confidence interval for the estimate of treatment difference in percentages will be estimated and constructed using the above-mentioned method.

## 9.2 SAMPLE SIZE DETERMINATION

A total of 100 participants will provide at least 90% power to detect a 15% difference in the percentage of time participants spend in deep and REM sleep, as quantified using the Whoop sleep-tracking device after the four-week treatment phase. The CRO 83Bar will recruit 8,000 potential study participants using social media, will screen approximately 800 study participants via online screening surveys, will contact 440 participants from a call center, and will ultimately enroll 150 qualified study participants. Based on our two previous clinical studies with Defined CBD, we anticipate a maximum dropout rate of 33% in Le Rêve 3.0.

## 9.3 POPULATIONS FOR ANALYSES

Analysis of the primary and second endpoints will be completed after all study participants have completed the 12-week study, outstanding data queries have been resolved or adjudicated as unresolvable, and the data have been cleaned and finalized. This analysis of the primary and secondary endpoints will serve as the final analysis of the endpoints. A safety analysis dataset will be composed of any AE and SAEs collected by the medical monitor in the form of eCRFs.

## 9.4 STATISTICAL ANALYSES

### 9.4.1 GENERAL APPROACH

For the primary and secondary endpoints, the difference in the means of each endpoint in participants that received Defined CBD and the placebo control at the end of the two four-week treatment phases will be compared using a 2-sided test with an alpha level at 0.05 to evaluate superiority. The p-value and 95% confidence interval for the estimate of treatment difference in percentages will be estimated and constructed using the above-mentioned method.

### 9.4.2 ANALYSIS OF THE PRIMARY EFFICACY ENDPOINT(S)

The primary endpoint that will be analyzed in Le Rêve 3.0 is the percentage of time study participants spend in deep and REM sleep as quantified using wrist-worn sleep-tracking device Whoop. The difference in the mean percentage of sleep spent in deep and REM sleep in participants that received Defined CBD and the placebo control at the end of the two four-week treatment phases will be compared using a 2-sided test with an alpha level at 0.05 to evaluate superiority. The p-value and 95% confidence interval for the estimate of treatment difference in percentages will be estimated and constructed using the above-mentioned method.

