## 1 PROTOCOL SUMMARY

### 1.1 PROTOCOL SYNOPSIS

**Study Title:** Le Rêve 3.0: A Double-Blind, Placebo-Controlled, Randomized, Crossover Investigational Study to Determine if Defined CBD, a Custom-Formulated Cannabidiol (CBD) Capsule, Influences Sleep Physiology.

**Study Description:** Insomnia is a disorder in which people have inadequate or poor-quality sleep due to a number of factors, such as difficulty falling asleep, waking up frequently during the night with difficulty returning to sleep, waking up too early in the morning, or having unrefreshing sleep. Defined CBD is a capsule composed of highly purified (>99.9% purity) hemp-derived CBD and terpenes (>98% purity). Defined CBD contains no  $\Delta$ -9-tetrahydrocannabinol ( $\Delta$ -9-THC). Our research study, entitled Le Rêve 3.0, is designed to evaluate the efficacy of Defined CBD on sleep physiology. This trial is not intended to treat, diagnose, prevent, or cure any disease.

**Objectives:** Primary Objectives: To determine if Defined CBD influences objective measures of sleep physiology.

[figure not shown]
Secondary Objectives: To determine if Defined CBD influences subjective measures of sleep physiology.

**Endpoints:** Primary Endpoint: The percentage of sleep spent in deep [slow wave sleep (SWS)] and rapid eye movement (REM) sleep as determined using an objective wrist-worn sleep-tracking device called Whoop.

Secondary Endpoints: Total sleep time, sleep latency, the number of sleep disturbances, time spent in each sleep stage, percentage of time spent in each sleep stage, and subjective measures of sleep physiology as collected via participant surveys.

Study Population:	We will enroll 150 study participants who display chronic insomnia defined as a self-reported difficulty initiating (latency to persistent sleep >30 min) and/or maintaining sleep (>30 min awake, or waking >30 min before desired waking time) on three or more nights per week for at least 3 months. Participants will also complete a brief clinically validated insomnia severity index, and only participants with an Insomnia Severity Index score >15 will be enrolled in Le Rêve 3.0. We will enroll males or females aged 25–70 years that are located in the United States that meet inclusion and exclusion criteria.
Phase:	N/A

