### 3 OBJECTIVES AND ENDPOINTS

OBJECTIVES	ENDPOINTS	JUSTIFICATION FOR ENDPOINTS
Primary		
The primary objective is to determine if Defined CBD influences objective measures of sleep physiology.	The primary endpoint is the percentage of time spent in slow wave (Deep) and REM sleep as quantified by a non-invasive wrist-worn sleep-tracking device called Whoop.	Deep and REM sleep are thought to contribute significantly to restorative sleep. We will use an unbiased approach to collect objective data on these sleep stages to determine if Defined CBD increases deep and REM sleep.
Secondary		
The secondary objective(s) are to determine if Defined CBD influences objective and subjective measures of sleep physiology.	Additional objective secondary outcome measures that will be collected on the Whoop device include: Total sleep time, sleep latency, the number of sleep disturbances, time spent in each sleep stage, and the percentage of time spent in each sleep stage.  A modified version of a clinically validated questionnaire entitled the Participant Global Impression (PGI)  will be used to track subjective measures of sleep physiology. This data will be collected from study participants in the form of a brief five-minute survey that will be completed on their smartphone at the end of each four-week treatment period. This survey measures the perception of the study participants of the effects of treatment.	Although some early clinical studies suggest that CBD might help people with insomnia, no studies have addressed if it influences objective and subjective measures of sleep physiology. Therefore, we will include a number of objective and subjective secondary outcome measures in this study to fill this void in knowledge.

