## 8 STUDY ASSESSMENTS AND PROCEDURES

### 8.1 EFFICACY ASSESSMENTS

We will enroll 150 study participants who display chronic insomnia defined as a self-reported difficulty initiating (latency to persistent sleep >30 min) and/or maintaining sleep (>30 min awake, or waking >30 min before desired waking time) on three or more nights per week for at least 3 months. Participants will also complete a brief clinically validated insomnia severity index, and only participants with an Insomnia Severity Index score >15 will be enrolled in Le Rêve 3.0. We will enroll males or females aged 25–70 years that are located in the United States that meet inclusion and exclusion criteria.

Le Rêve 3.0 will be conducted in an entirely decentralized manner. Primary data for Le Rêve 3.0 will be obtained in a completely unbiased manner from a non-invasive sleep-tracking wrist-worn device called “Whoop” (<https://www.whoop.com>), that electronically collects and transmits sleep data from study participants in the comfort of their own beds.

The wristband collects hundreds of data points per second from a 3-axis accelerometer, 3-axis gyroscope, and heart rate sensor. The wristband can accurately measure the latency to fall asleep, total sleep time, sleep fragmentation, as well as the time spent in each sleep stage [Light, Slow Wave (Deep), Rapid Eye Movement (REM), and Awake]. The device also collects data using photoplethysmography (PPG), a technique that involves measuring blood flow by assessing superficial changes in blood volume. Heart rate, heart rate variability and respiratory rate, can all be derived from PPG data, and all of these metrics are used in Whoop’s sleep detection and staging algorithms. Importantly, two recent publications, published independently from Whoop, show that data on sleep stages collected from the Whoop device are highly accurate and correlate well with polysomnography (PSG), the gold-standard of sleep tracking used in clinical studies conducted in sleep clinics.

The primary endpoint efficacy endpoint in Le Rêve 3.0 is the percentage of time spent in slow wave (Deep) and REM sleep as collected by a non-invasive wrist-worn sleep-tracking device called Whoop. Additional objective secondary outcome measures that will be collected on the Whoop device include: Total sleep time, sleep latency, the number of sleep disturbances, time spent in each sleep stage, and the percentage of time spent in each sleep stage.

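### Does the mix of share of sleep and share of time, with no written formula for deep plus REM, leave the primary endpoint undefined?

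*Combined protocol and SAP*

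**What the plan says.** The primary endpoint is worded in two ways.

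- **Share of sleep.** The synopsis (section 1.1) has "The percentage of sleep spent in deep [slow wave sleep (SWS)] and rapid eye movement (REM) sleep". The null hypothesis (section 9.1) is that "there is no difference in the percentage of sleep spent in deep and REM sleep in participants that received Defined CBD" and those on placebo. The sentence in section 9.4.2 that states the comparison has "The difference in the mean percentage of sleep spent in deep and REM sleep".
- **Share of time.** Section 3 has "the percentage of time spent in slow wave (Deep) and REM sleep as quantified by a non-invasive wrist-worn sleep-tracking device". Section 4.1 hypothesises that the product "will increase the percentage of time participants spend in deep (SWS) and REM sleep". Section 8.1 has "the percentage of time spent in slow wave (Deep) and REM sleep as collected by a non-invasive wrist-worn sleep-tracking device". Section 9.2 sizes the trial "to detect a 15% difference in the percentage of time participants spend in deep and REM sleep". The opening sentence of section 9.4.2 has "the percentage of time study participants spend in deep and REM sleep as quantified using wrist-worn sleep-tracking device Whoop".

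Sections 4.1 and 8.1 list the device's stages as light, deep, REM and awake. The time and the percentage in each stage are secondary endpoints (sections 1.1, 3, 8.1, 9.1 and 9.4.3; section 8.1 does not use percentage of sleep for them either). In the readable text the sum of deep and REM is spelled out only in the conclusions drawn from the earlier studies (section 4.2), as a gloss on restorative sleep. The comparison is a two-sided test at 0.05.

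**The concern.** A primary endpoint that is a ratio needs a fixed top and bottom. Here the bottom changes name between sections, and inside section 9.4.2 it changes between adjacent sentences. Because the device also records wake, a share of time could be read as a share of time in bed. The top is given only as deep and REM, joined by a conjunction, which could be read as a sum or as two quantities.

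The population makes wake time relevant: eligibility rests on more than 30 minutes to fall asleep, more than 30 minutes awake in the night, or waking more than 30 minutes early. If treatment turned wake into mostly light sleep, deep plus REM could fall as a share of sleep and rise as a share of time in bed. If the definition were chosen after the data were seen, the estimate and even its sign could depend on that choice. For the numerator, the earlier studies reported REM, deep and restorative sleep separately, and not all reached significance.

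**Working it through.** **1. The plan's own figures.** Section 9.2 gives 100 participants for at least 90% power, 150 enrolled and at most 33% dropout. Enrolment reproduces: 100 / (1 - 0.33) = 149.3, rounded up to 150. The 100 cannot be reproduced under either denominator, because section 9.2 gives no SD, no baseline and no statement of whether 15% is absolute or relative. That gap is there however the endpoint is worded.

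**2. Denominator, from the text.** The two statements that fix what is tested are the null hypothesis in section 9.1 and the comparison sentence in section 9.4.2. Both say sleep, and the synopsis endpoint agrees. The time wording appears where the endpoint is described or the study introduced. Section 9.4.2 uses both phrases for one quantity in consecutive sentences, which is how loose synonyms are used. No section names time in bed or recording time as a denominator.

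**3. Numerator, from the text.** The endpoint is singular: one percentage. The individual stages' percentages are listed as secondary, so treating deep and REM as two primary endpoints would make the same variables both primary and secondary. The justification column in section 3 ties the two stages to restorative sleep, which section 4.2 glosses as their sum. The reading is therefore 100 x (deep + REM minutes) / (light + deep + REM minutes).

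**4. What would be at stake if the denominator really were open.** The minutes below are hypothetical, not from the documents: 480 in bed, 120 awake, 360 asleep, 144 in deep plus REM. Treatment turns 30 wake minutes into sleep, of which a fraction f is deep plus REM.

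- Share of sleep: before, 144/360 = 40.0%; after, (144 + 30f)/390.
- Share of time in bed: before, 144/480 = 30.0%; after, (144 + 30f)/480.

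| f | Share of sleep, change | Share of time in bed, change |
|---|---|---|
| 0.1 | 147/390 = 37.69%, -2.31 | 147/480 = 30.62%, +0.62 |
| 0.2 | 150/390 = 38.46%, -1.54 | 150/480 = 31.25%, +1.25 |
| 0.3 | 153/390 = 39.23%, -0.77 | 153/480 = 31.88%, +1.88 |
| 0.4 | 156/390 = 40.00%, 0.00 | 156/480 = 32.50%, +2.50 |

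With 45 minutes awake, 174 in deep plus REM and f = 0.2, the share of sleep goes from 174/435 = 40.0% to 180/465 = 38.71% (-1.29). The share of time in bed goes from 174/480 = 36.25% to 180/480 = 37.50% (+1.25).

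The signs differ only when the added sleep is poorer in deep plus REM than the baseline 40%. Nor would the two analyses necessarily give opposite test results. With 100 pairs, t = 1.984 and a standard error of SD/10, the -1.54 is significant only if the SD of within-person differences is below 1.54 x 10 / 1.984, about 7.8 points. The +1.25 needs an SD below 1.25 x 10 / 1.984 = 6.3 points. The plan gives no SD.

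**5. What would be at stake if the numerator really were open.** If deep and REM were each tested at 0.05 and either counted as success, the false-positive rate would be 1 - 0.95 x 0.95 = 9.75% for independent tests. The plan contains no such rule, so this figure does not describe the trial.

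**The case for a change.** The strongest case for a change has three parts.

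First, the protocol lists awake among the stages and makes the percentage of time in each stage a secondary endpoint. A percentage for awake needs a denominator that includes wake, so share of time can mean something other than share of sleep in the protocol's own vocabulary. That stands for the secondary awake percentage. It does not carry over to the primary comparison, where the hypothesis and test sentences both say sleep.

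Second, the sponsor has a term for the sum and does not use it to define the endpoint, although the choice mattered in its own data: in Le Rêve 2.0 restorative sleep reached significance and REM did not; in the combined data REM and restorative sleep did and deep sleep did not. This shows the numerator is consequential, not that it is open. The singular endpoint and the secondary status of individual stages still leave one coherent reading. The plural reference to stages in section 3 is ordinary grammar for two stages. Part of the account of the earlier studies and their figures cannot be read in the public copy, so nothing can be argued from their silence.

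Third, a confirmatory endpoint should not rest on inference. As a drafting principle that is right, and one phrase with one formula would be tidier. But a later switch to time in bed would visibly depart from the null hypothesis in section 9.1, so the text already constrains the analyst.

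**Conclusion.** The wording is inconsistent and the formula is never written out, but this does not call for a change to the plan. An analyst who follows sections 9.1 and 9.4.2 would compute deep plus REM over total sleep, wake excluded, and test it once, two-sided at 0.05. Writing that down would record what the plan already implies and would leave the data collected and the test as they are.

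The sizes above are illustrative only. The sign change (-1.54 against +1.25 points) rests on invented minutes, a denominator no section names, and added sleep poorer in deep plus REM than baseline. The 9.75% rests on a success rule the plan does not contain. The conclusion assumes that share of time in sections 3, 4.1, 8.1 and 9.2 is a loose synonym for share of sleep, as the adjacent sentences of section 9.4.2 indicate. The unstated scale of the 15% in section 9.2 belongs to the sample-size section and is not settled here.
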